## D Study Design

### D1 Overview or Design Summary

This is a rs16969968 based stratified randomized controlled trial design examining the effects of one experimental factor (combination NRT vs. varenicline vs. placebo for 3 months) and one non-experimental participant characteristic: *CHRNA5* genotypes associated with high, intermediate, and low risk levels for nicotine dependence and cessation failure. Based on the frequency distribution of these genotypes, there will be sufficient numbers of each genetic groups represented in the active and placebo arm. We will examine the main effects of medication (cNRT vs placebo as well as varenicline vs. placebo) and genotypes (high, intermediate, and low risk), as well as the pharmacogenetic interaction between the genotypes and medication on the primary cessation outcome (abstinence at end of treatment, ABST\_EOT) and other outcomes (abstinence at 6 months and 1 year). We choose the primary efficacy measure of abstinence at 3 month (EOT) because our preliminary data from the UW-TTURC trial suggest the genetic effects on cessation take place in the early cessation stage. Our hypothesis is that NRT significantly increases smoking abstinence in patients possessing high-risk genotypes, but not amongst patients without such genotypes.

This experiment will achieve Aims 1 and 2 by answering the following questions:

- 1) Is there a genotype X Pharmacotherapy (cNRT vs. placebo) interaction with regard to abstinence?
- 2) Is there a genotype X Pharmacotherapy (varenicline vs. placebo) interaction with regard to abstinence?

### D2 Subject Selection and Withdrawal

Some subjects for this study have participated in the previous study: the Collaborative Genetic Study of Nicotine Dependence (COGEND). Subjects who participated in COGEND must have provided a DNA sample. Subjects must have given permission to share data and to be contacted for future studies for both COGEND. Subjects must have active nicotine dependence. We are expanding enrollment opportunities to the community, by recruiting from the volunteers for health program, and smokers interested in smoking cessation in the local community. These participants must give permission to share data. When participants agree to be part of this study he/she gives up any property rights he/she may have in the blood and data. Cells from the blood will be used to develop cell lines. DNA and plasma will then be extracted from these cell lines and used for research purposes. We will use the blood sample (DNA, plasma, cell lines from blood), and data for other research projects in the future.

#### 2.a Inclusion Criteria

Inclusion:

- 1) Adult (>=21 years of age), seeking treatment for smoking cessation.
- 2) Able to speak English,
- 3) Active smoking (Cigarettes Per Day (CPD) >=5) and exhaled CO >=8 ppm
- 4) Agree to participate in this randomized smoking cessation trial with follow up assessments up to 12 months, and

---

## 2.a Exclusion Criteria

### Exclusion:

The subject will be excluded for having a condition that prevents him/her from effectively participating in the protocol.

- 1) Pregnancy or breast feeding,
- 2) Active use or recent use (<= to 1 month) of medication or e-cigarettes for nicotine dependence/smoking cessation, or use of e-cigarettes for more than 9 days in the prior month
- 3) Allergy to Nicotine patch, Nicotine lozenge, or varenicline
- 4) Unwillingness to prevent pregnancy during the medication phase and 1 month afterwards (women only),
- 5) Significant cardiac conditions (myocardial infarction (heart attack), unstable angina, coronary angioplasty, cardiac bypass) or serious arrhythmia within 6 months
- 6) Current heavy alcohol consumption (greater than or equal to 6 drinks/day, 6 days/week)
- 7) Active psychosis or poorly controlled depression in the past 6 months
- 8) Any suicide attempt or poorly controlled depression in the past 6 months,
- 9) End stage renal disease with hemodialysis

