### Step 2. Ask the potential participant the following screening questions to determine eligibility.

- 1) How many cigarettes do you smoke a day?
- 2) Are you committed to participating in this study on treatment for smoking cessation for a full year?
- 3) Are you willing to use birth control for 3 months while you are receiving medication treatment for smoking cessation and one month after? (ONLY for pre-menopausal women)
- 4) Are you pregnant or breast feeding? (ONLY for pre-menopausal women)
- 5) Do you currently take the medication Bupropion, Wellbutrin, Zyban, Varenicline, or Chantix, or nicotine patch or lozenge?
- 6) Are you allergic to the Nicotine Patch, lozenge, or varenicline?
- 7) Did you have significant cardiac conditions (an acute heart attack, unstable angina, coronary angioplasty, cardiac bypass) in the past 6 months?
- 8) Do you currently drink alcohol at the level of at least 6 drinks per day, 6 days per week?

---

- 9) Have you had active depression or psychosis in the past 6 months?
- 10) Do you currently have thoughts of suicide or have a suicide attempt in the past 6 months?
- 11) Do you have end stage kidney disease requiring hemodialysis?

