#### Step 4. Obtain Informed Consent

Patients who express interest in participating will be informed in greater detail about the study and receive screening for eligibility criteria by the PI psychiatrist or the research assistant. The patients will learn about general requirements for participation (e.g., need for follow-up, participation in assessments, etc.) as well as risks associated with nicotine toxicity, nicotine withdrawal, blood sample and pharmacotherapy. If still interested and eligible, the patients will then be asked to provide written informed consent to participate, on a form approved by the Washington University School of Medicine Institutional Review Board. Study candidates will read the informed consent document and be given an opportunity to ask any questions regarding study participation. They will also complete the consent form. A follow up contact can be scheduled if potential participants would like to have more time to consider participation. Participants will receive a signed copy of the consent document.

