### **2.d Randomization Method and Blinding**

The participants will be randomized with the ratio 1:1:1 to the treatment arm of combination NRT (nicotine patch and lozenge) plus smoking cessation counseling, or the treatment arm of varenicline plus smoking cessation counseling, or the treatment arm of placebo (patch and lozenge or pill) plus smoking cessation counseling.

Participants will be randomly assigned to 1) combination NRT plus counseling, 2) varenicline plus counseling, or 3) placebo plus counseling. SAS Version 9 statistical software will be used to generate the random assignment table stratified by CHRNA5 genotype rs16969968. The group assignment and genotype will be coded to ensure that the double blind is maintained, and the interface will prevent staff from having access to the participant's assignment and genotype until after the baseline and post treatment assessments have been completed.

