### **2.e Risks and Benefits**

Risks associated with this research are judged to be minimal.

Smoking withdrawal is associated with a number of unpleasant symptoms such as sleep disturbance, hunger, craving, and negative mood. Most smokers have tried to quit in the past and are familiar with these phenomena.

With respect to the pharmacotherapy, participants will be made aware of the common side effects before they consent to participate in the study. It should be noted that the nicotine patch and lozenge are available over the counter. The nicotine patch has very few side effects, but participants may have a local skin reaction, and rarely, individuals may have a more systematic

---

allergic reaction. The most common side-effects associated with the nicotine patch are diarrhea, indigestion, nausea and vomiting, dry mouth, muscle and joint pain, sleeplessness, and abnormal dreams. Side effects associated with wearing an adhesive patch include skin rash, redness, and itching or irritation of the skin. The most likely side effects associated with the nicotine lozenge are heart burn, hiccup, nausea, upper respiratory track infection, coughing, and sore throat. In most cases, these side effects have been mild to moderate in intensity and go away once the patch is removed. Although most smokers have tolerance to nicotine, symptoms of acute nicotine toxicity (nausea and vomiting) are possible.

Varenicline is approved by the FDA for smoking cessation and is medically safe for most smokers except for individuals with severe (end stage) kidney failure or hypersensitivity to varenicline. In addition, although no causal relationship has been established, current labeling for varenicline (FDA, 2011) recommends monitoring for serious neuropsychiatric symptoms including changes in behavior, agitation, depressed mood, suicidal ideation, and suicidal behavior. Varenicline labeling also notes that some individuals with pre-existing psychiatric conditions may experience worsening of their conditions. Preliminary data from the University of Wisconsin Center for Tobacco Research and Intervention (UW-CTRI) smoking cessation trials showed comparable rates of discontinuation and adverse events due to NRT and varenicline. The low rate of serious adverse events is consistent with recent data on the safety of varenicline.

Blood draw may result in bruising, and very rarely, infection at the site of needle stick.

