Study participants will be closely monitored in accordance with current FDA recommendations as well as the consensus recommendations of the 2008 Guideline Panel which provides additional detailed instructions for clinicians regarding all FDA approved smoking cessation medications. We will follow the patient instruction and adverse events monitoring procedures used in the University of Wisconsin Center for Tobacco Research and Intervention (UW-CTRI). Patient education about possible side effects, access to a medication hotline, and ongoing monitoring will be consistent with FDA recommendations, clinical practice guidelines, and procedures successfully used in prior and ongoing UW-CTRI research using varenicline and combination NRT. This protocol is consistent with the 2010 FDA warning and recommendations for monitoring requirements regarding the black box warning of psychiatric risk for varenicline. In addition, we will make appropriate changes in study procedures if the FDA issues updates on varenicline.

All medical information and data from the interviews will be kept in a locked file cabinet in a locked office and identified by a code number. The master list of subject names will be kept in a separate locked file cabinet in a separate locked office by the Principal Investigator. Computerized research data are identified only by subject identification numbers and codes, and confidential data files are password protected. Written records of counseling sessions and audio recordings of sessions will be kept in a locked cabinet and will be destroyed within one year of the termination of the project. Audio recordings will be obtained if authorized by the participant. Only authorized individuals will be permitted to review these records. We have followed these procedures in the past without any breeches of confidentiality, and we feel certain that we will be able to maintain the same level of security for this project.

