## **2.g When and How to Withdraw Subjects**

We are conducting this research with strong safety measures in place (close monitoring and screening) to gather the needed data without imposing unacceptable risks. The participants will remain under the care of their own physician(s) throughout the study. To facilitate safety, participants who are not medically appropriate to take combination NRT or varenicline will not be included in the study (see exclusion criteria). Once enrolled, follow-up protocols will assess the presence of medication side effects and unanticipated health events at all study visits and follow-up contacts. We will recommend dosage/use alternations as per good clinical practice if the patient experiences symptoms of nicotine toxicity or other troublesome side effects once they begin medication treatment. We will refer patients to the study physician as needed.

Participants' medications will be continued if they have relapsed to smoking regularly. Subjects with symptoms of nicotine toxicity (including diarrhea, abdominal pain, vomiting, dizziness, and headache) reported at any research contact will be told to discontinue their medication immediately until they have a chance to discuss their symptoms with the study physician ([name]) or their primary care doctor, who will decide upon a course of action based upon the patient's status and risk (e.g., a dose reduction or medication discontinuation). Emergency care will be administered as needed. If the only severe symptom is sleep disturbance, subjects will be instructed to remove the patch at night, but otherwise keep receiving treatment according to the protocol. Should either excessive risk to study participants and/or lack of measurable benefit to study participants be determined, the study will be stopped and all participants notified in a manner appropriate to the nature of the risk and/or lack of benefit.

Any patient who reports discomfort as a result of completing the assessment of depression and anxiety will be reminded that the evaluation is discretionary, that it will be discontinued if the patient wishes, and that doing so will not affect the patient's medical care. The experienced psychiatrist investigator will be on call in case a patient has an adverse reaction to a screening or outcome evaluation. We have administered these tests to over 2,500 patients without a single subject reporting more than mild, transient emotional distress.

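### The listed kidney exclusion and its screening question cover only hemodialysis, which is narrower than the protocol's own varenicline exception for end-stage kidney failure

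*Combined protocol and SAP*

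**What the plan says.** Four parts of the protocol bear on kidney disease and varenicline.

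- **Section D2 2.a, exclusion 9:** "End stage renal disease with hemodialysis".
- **Section D2 2.c, Step 2, question 11, repeated in section E1, Step 2:** "Do you have end stage kidney disease requiring hemodialysis".
- **Section D2 2.e:** varenicline is described as "medically safe for most smokers except for individuals with severe (end stage) kidney failure or hypersensitivity to varenicline".
- **Section D2 2.g:** as a safety measure, "participants who are not medically appropriate to take combination NRT or varenicline will not be included in the study (see exclusion criteria".

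The exclusion list in 2.a opens with a general sentence: "The subject will be excluded for having a condition that prevents him/her from effectively participating in the protocol". Under 2.c Step 4, candidates "receive screening for eligibility criteria by the PI psychiatrist or the research assistant". Under 2.d, "The participants will be randomized with the ratio 1:1:1" to combination NRT, varenicline or placebo.

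**The concern.** Section 2.e names two groups to whom its safety statement on varenicline does not extend. One is people hypersensitive to the drug; exclusion 3 and screening question 6 carry that over, as allergy, without further condition. The other is people with end-stage kidney failure, and there the eligibility text adds a condition that 2.e does not have: hemodialysis. A screener who applies the written list and script exactly could therefore admit someone whom the protocol itself sets outside its safety statement.

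What is at stake is the safety of an individual participant. Eligibility may be screened by a research assistant, so the literal wording carries weight. Treatment is also double-blind, so staff would not ordinarily know that such a participant was taking varenicline.

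**Working it through.** The protocol states no figure to reproduce here. The check is a comparison of wordings, with one line of arithmetic.

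**Step 1. Apply each wording to three kinds of end-stage patient.**

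| Patient with end-stage disease | 2.e exception | Exclusion 9 | Question 11 |
|---|---|---|---|
| On hemodialysis | Covered | Excluded | Yes |
| On another form of dialysis | Covered | Not excluded | No |
| Not yet dialysed | Covered | Not excluded | Depends on how *requiring* is read |

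The second row is the clear gap: such a person can truthfully answer no to question 11 and matches none of the nine listed exclusions on account of the kidney disease. The third row is partly closed. Exclusion 9 says *with*, which points to receipt of hemodialysis. Question 11 says *requiring*, which points to need and may catch some people who have not started. The criterion and its question therefore also differ from each other.

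**Step 2. Look for other text that would catch the second row.**

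- The opening sentence of 2.a is about ability to take part effectively. It leaves room for judgement but names no renal condition.
- The sentence in 2.g states the right intent, but refers the reader back to the exclusion criteria to carry it out.
- In 2.e, "Study participants will be closely monitored in accordance with current FDA recommendations" governs people already enrolled, not who may enrol.
- The schedule in E2 lists no kidney-function test; its text assigns the blood sample to nicotine metabolism and genetic markers.
- E2 and E3 include a medical history, which may bring a case to light, but no written criterion attaches an exclusion to it.
- The regimen in D3 3.b takes varenicline to 1 mg twice daily and states no renal adjustment.
- The Baseline Interview (K2) and Screening Log (K7) are listed but not reproduced, so they may contain further renal questions.

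In the visible text, the listed criteria and the screening script are thus the only specific renal safeguard.

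**Step 3. Chance of exposure for such an enrolee.** Inputs: 822 participants (section C1) and 1:1:1 allocation (section 2.d).

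- Per arm: 822 / 3 = 274.
- Probability of varenicline: 274 / 822 = 1/3, or about 0.333.

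This is a probability per person. The documents give no prevalence of end-stage disease managed without hemodialysis, so no head count can be derived.

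**The case against.** The strongest reply is that 2.e is a risk narrative and not an eligibility rule, and that all three wordings loosely describe one intended group. The items under the opening sentence of 2.a include pregnancy, drug allergy and recent cardiac events, so the protocol evidently treats drug safety as part of being able to participate. Taking part means accepting any of the three arms, and someone who cannot safely take one of them can reasonably be turned away under that sentence. Section 2.g states that intent openly. In addition, hemodialysis is something a lay respondent can report and a research assistant can record, whereas disease stage is harder to self-report.

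Much of this stands. A reader might infer that the protocol makes these patients eligible outright, or that some will be given varenicline. The documents do not support either inference: an investigator can still exclude them on judgement, and forms not reproduced may ask more. The point holds only for the enumerated criteria and the screening script. The remark about a recognisable cue also stands, and it argues for broadening the wording and not merely striking the dialysis words.

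The reply does not remove the mismatch. If hemodialysis was only shorthand, broader wording changes nothing that was intended. If it was a deliberate limit, the difference from 2.e needs a reason, and none is given.

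**Conclusion.** The concern holds as a minor patient-safety correction. Under the listed criteria and the script, the kidney exclusion is narrower than the exception in 2.e. A person with end-stage disease managed without hemodialysis meets no listed exclusion and could be randomized with a 1/3 chance of varenicline, unless excluded on judgement.

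This rests on two readings: that *severe (end stage)* in 2.e means end-stage disease as such, and that the forms not reproduced add no renal bar. The mismatch in wording is certain; actual enrolment of such a person is not. The group is probably very small and may be empty. Sample size, power, alpha and the primary analysis are unaffected.

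A reader might also infer that the trial needs a kidney-function test, or a bar on milder renal impairment. The documents do not support that: the only renal limit they attach to varenicline is end-stage failure.

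**What to change.** Change the wording in three places.

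- **Section D2 2.a, exclusion 9:** 'End stage renal disease, whether or not on dialysis'.
- **Section D2 2.c, Step 2, question 11, and section E1, Step 2, question 11:** 'Do you have end stage kidney disease, or are you on any form of dialysis?'

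The criterion then matches 2.e, the cross-reference in 2.g leads to a list that covers the kidney exception in full, and the question keeps dialysis as a cue that respondents recognise. If K2 or K7 repeats the question, it should be aligned there too.

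The cost is a wording amendment, with no new test, visit or analysis. The downside is possibly a few extra screen failures. The criterion would still rest on self-report, as it does now.

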## 2.b Ethical Considerations

This study will recruit from all eligible subjects regardless of their age, gender, and ethnicity. No children or pregnant women will be included in this study.

## 2.c Subject Recruitment Plans and Consent Process

We propose to enroll previous participants of the COGEND study, VFH, and the local community. We expect we can successfully recruit 822 patients in 3 years.

### Step 1. Screening of Potentially Eligible Subjects

The PI or research assistant will need to access the following data element.

- 1) Subject agreed to be contacted to participate in a smoking cessation trial.

### Step 2. Ask the potential participant the following screening questions to determine eligibility.

- 1) How many cigarettes do you smoke a day?
- 2) Are you committed to participating in this study on treatment for smoking cessation for a full year?
- 3) Are you willing to use birth control for 3 months while you are receiving medication treatment for smoking cessation and one month after? (ONLY for pre-menopausal women)
- 4) Are you pregnant or breast feeding? (ONLY for pre-menopausal women)
- 5) Do you currently take the medication Bupropion, Wellbutrin, Zyban, Varenicline, or Chantix, or nicotine patch or lozenge?
- 6) Are you allergic to the Nicotine Patch, lozenge, or varenicline?
- 7) Did you have significant cardiac conditions (an acute heart attack, unstable angina, coronary angioplasty, cardiac bypass) in the past 6 months?
- 8) Do you currently drink alcohol at the level of at least 6 drinks per day, 6 days per week?

---

- 9) Have you had active depression or psychosis in the past 6 months?
- 10) Do you currently have thoughts of suicide or have a suicide attempt in the past 6 months?
- 11) Do you have end stage kidney disease requiring hemodialysis?

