### **3.b Treatment Regimen**

During the baseline visit (visit 1), all participants will be randomized at 1:1:1 to 1) one arm of combination nicotine and smoking cessation counseling, or 2) varenicline and smoking cessation counseling, and 3) another arm of placebo and smoking cessation counseling at no cost to participants. Participants will receive enough patches to last 12 weeks. The duration of medication treatment is 12 weeks (standard for participants who smoke >9 cigs/day=8 weeks of 21mg, 2 weeks of 14mg, and 2 weeks of 7mg nicotine patches; standard for participants who smoke 5-9 cigs/day=8 weeks of 14mg and 4 weeks of 7mg;).

**Nicotine Lozenge:** The 4 mg dosage is recommended for patients who take their first cigarette within 30 minutes of waking and the 2mg dosage is recommended for patients who take their first cigarette more than 30 minutes after waking. Participants will begin taking lozenges a week before abstinence to replace some cigarettes. Participants will then take 1 lozenge every 1-2 hours for 6 weeks, then 1 lozenge every 2-4 hours for 3 weeks, and 1 lozenge for every 4-8 hours for 3 weeks. Participants will be encouraged to take a minimum of 4 pieces/day unless this amount produces adverse effects.

**Varenicline:** Varenicline will be initiated with a titration for 7 days before the quit date. Before the quit date, participants will take one 0.5mg tablet daily for 3 days, then two 0.5mg tablets for 4 days (one in the morning and one in the evening). After the quit date (day 8), participants will take 1mg tablet in the morning and in the evening.

**Placebo:** 50% of participants assigned to the placebo group will receive placebo patch/lozenge, and 50% will receive the placebo pill as a control for the two active medication arms.

All participants will be given complete instructions on proper medication use, and will be urged to contact his/her physician and a study hotline number immediately in case of listed symptoms of nicotine toxicity or side effects. Dose changes or discontinuation of NRT may be recommended; all changes will be addressed in analyses of adherence outcomes.

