### **3.i Receiving, Storage, Dispensing and Return**

Participants will receive their study medication when they attend the in office visit 1 (baseline).

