#### Step 2. Ask the potential participant the following screening questions to determine eligibility.

- 1) How many cigarettes do you smoke a day?
- 2) Are you committed to participating in this study on treatment for smoking cessation for a full year?
- 3) Are you willing to use birth control for 2 months while you are receiving medication treatment for smoking cessation? (ONLY for pre-menopausal women)
- 4) Are you pregnant or breast feeding? (ONLY for pre-menopausal women)
- 5) Do you currently take the medication Bupropion, Wellbutrin, Zyban, Varenicline, or Chantix?
- 6) Are you allergic to the Nicotine Patch, lozenge, or varenicline?
- 7) Have you had significant cardiac conditions (heart attack, unstable angina, coronary angioplasty, cardiac bypass) in the past 6 months?
- 8) Do you currently drink alcohol at the level of at least 6 drinks/day, 6 days/week?
- 9) Have you had active depression or psychosis in the past 12 months?
- 10) Do you currently have thoughts of suicide or have a prior suicide attempt in the past 12 months?
- 11) Do you have end stage kidney disease requiring hemodialysis?

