## ***E2 Schedule of Measurements***

Participants will receive a baseline assessment of smoking history and withdrawal symptoms, provide a breath sample for alveolar CO level, provide blood sample for assessments of nicotine metabolism and genetic markers, receive smoking cessation counseling, and be randomized to one of two groups (transdermal nicotine replacement therapy and counseling vs placebo and counseling). These evaluations will be conducted by the Principal Investigator [name] or a research assistant. The baseline assessment will take approximately 90 minutes. Participants will be asked to also participate in 8 follow up visits, two in person at 3 months (if biochemical verification is needed) and 6 months (if biochemical verification is needed) and the rest by phone at the last pre-quit, quit date, 1 week, 2 weeks, 4 weeks, 3 months (if biochemical verification is not needed), 6 months (if biochemical verification is not needed) and 1 year after the quit date.

	office	office	phone	phone	phone	phone	phone	office/phone	office/phone	phone
Reimbursement	\$25	\$25/\$40	N/A	N/A	N/A	N/A	N/A	\$40/\$20	\$40/\$20	\$10
Visit Number	Pre- Visit	Visit 1	Visit 2	Visit 3	Visit 4	Visit 5	Visit 6	Visit 7	Visit 8	Visit 9
Visit description	Initial Visit	Baseline	pre-quit	quit day	wk 1 post quit	wk2 post quit	wk4 post quit	wk12 post quit	wk26 post quit	wk52 post quit
IF GENOTYPE DATA IS NEEDED										
Blood Sample	X									
SSAND	X									
Realm-R	X									
Measurement of expired breath CO	X									
ASSESSMENTS										
Screening Questions at Baseline (before consent)		X								
Contact Information Form		X								
Baseline Assessment (Demographics/smoking status/Tobacco History/ Environmental History/ Brief Medical history)										
Brief WISDM37	X									
Measurement of expired breath CO	X							X**	X**	
WSWS	X	X*	X	X*	X*	X*	X*	X	X*	X*
Adverse Event Assessment	X	X*	X*	X*	X*	X*	X*	X		
Follow-up Assessment (smoking status, Timeline follow back, environmental factors)		X	X	X	X	X	X	X	X	X
Pill/Medicine Count								X		
Expectations								X		
Adherence self reported		X	X	X	X	X	X	X		
INTERVENTION COMPONENTS										
Approximate Counseling (minutes)	15	10	10	10	10	10	10	10		
Medication (cNRT, varenicline, placebo)	X	X	X	X	X	X	X			
Blood Sample- if pre-visit was not needed	X									

\*indicates a brief version of assessment; \*\*if self-reported abstinence CO data for biochemical confirmation

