#### **4.b Medical Monitoring**

The principal investigator will be responsible for routine monitoring of the trial's progress. This monitoring includes scheduled biweekly meetings with study staff and review of written documentation. Data that are reviewed at these meetings include the number and type of participants enrolled, the number and reasons for exclusions from enrollment, the number of participants treated and the stage of intervention, a summary and an individual review of any unanticipated health events, and outcome data. In addition, any unanticipated health events that raise concerns (e.g., allergic reaction, symptoms suggestive of nicotine toxicity) will be immediately reported to the study physicians (PI psychiatrist).

To facilitate participant safety, study participants must meet study inclusion and exclusion criteria. Once enrolled, follow-up protocols will assess the presence of medication side effects and unanticipated health events at all study visits and follow-up contacts. We will recommend dosage/use alterations as per good clinical practice if the patient experiences symptoms of nicotine toxicity or other troublesome side effects. We will refer patients to the study physician as needed.

If participants are smoking regularly, we will tell them to continue taking the study medication and set another quit date as soon as possible. Should either excessive risk to study participants and/or lack of measurable benefit to study participants be determined, the study will be stopped and all participants notified in a manner appropriate to the nature of the risk and/or lack of benefit.

---

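### Exclusion 5 bars a recent serious arrhythmia, but both copies of screening question 7 leave it out, and no other step in the available text names it

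*Combined protocol and SAP*

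**What the plan says.** The criterion is item 5 of the exclusion list in D2, 2.a: "Significant cardiac conditions (myocardial infarction (heart attack), unstable angina, coronary angioplasty, cardiac bypass) or serious arrhythmia within 6 months".

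The protocol gives the screening script twice, each time under a Step 2 whose stated purpose is to establish eligibility. In D2, 2.c, question 7 reads "Did you have significant cardiac conditions (an acute heart attack, unstable angina, coronary angioplasty, cardiac bypass) in the past 6 months". In E1, question 7 reads "Have you had significant cardiac conditions (heart attack, unstable angina, coronary angioplasty, cardiac bypass) in the past 6 months".

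Two further provisions bear on the point. At the consent step (D2, 2.c, Step 4, repeated in E1, Step 3) candidates "receive screening for eligibility criteria by the PI psychiatrist or the research assistant". Section E4, 4.b adds: "To facilitate participant safety, study participants must meet study inclusion and exclusion criteria". F2 and H1 repeat that requirement.

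On timing, the schedule in E2 places the screening questions at baseline, ahead of consent. Allocation comes at the same visit: "During the baseline visit (visit 1), all participants will be randomized at 1:1:1" (D3, 3.b). D3, 3.i has study medication handed out at that visit too.

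**The concern.** A screening question written to apply a criterion should ask about everything the criterion covers. Question 7 is plainly the question for exclusion 5: it uses the same opening phrase, the same four conditions and the same 6-month window. It stops before the arrhythmia clause.

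What is at stake is safety. A research assistant may do the screening, and screening, randomisation and dispensing are all placed at Visit 1. If nothing beyond the script drew out the information, a candidate with a recent serious arrhythmia could answer no to question 7 and be given study drug, although the protocol excludes that person. D2, 2.g relies on the exclusion criteria to keep out people medically unsuited to either active treatment, and D2, 2.e notes a regulatory warning about varenicline in cardiac patients.

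**Working it through.** No formula applies, and the plan states no figure to reproduce. The check sets the criterion beside the two questions and then looks for any other step that names the missing item.

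**Item by item**

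| Element of exclusion 5 | Question 7, D2 2.c | Question 7, E1 |
|---|---|---|
| Myocardial infarction | asked | asked |
| Unstable angina | asked | asked |
| Coronary angioplasty | asked | asked |
| Cardiac bypass | asked | asked |
| Serious arrhythmia | not asked | not asked |
| 6-month window | same | same |

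Each copy covers 4 of 5 conditions. The same one is missing in 2 of 2 copies.

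**Does the script otherwise follow the exclusion list?** Matching the nine exclusions to the D2, 2.c questions gives:

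- Asked in full: 1 (question 4), 3 (question 6), 4 (question 3), 6 (question 8), 7 (question 9), 8 (questions 9 and 10) and 9 (question 11).
- Asked in part: 2 (question 5 covers current use only and does not mention e-cigarettes) and 5 (question 7, no arrhythmia).

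That is 7 + 2 = 9 of 9 exclusions with a matching question, 7 in full and 2 in part. The count is for the D2, 2.c copy only. The E1 copy differs on other points, such as the contraception period and the psychiatric look-back. This point is confined to exclusion 5.

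**Does any other step name arrhythmia?** The word occurs once in the documents, in exclusion 5. The steps that might still bring it out are all general:

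- the eligibility screening at consent (D2, 2.c, Step 4; E1, Step 3);
- the health questions at the initial visit, for those who attend one, and the medical history at Visit 1 (E3);
- the Baseline Interview (K2) and Screening Log (K7), which section K lists by title without showing their contents.

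The schedule in E2 lists no ECG and no review of medical records. The text does not say that the Visit 1 history is compared with exclusion 5 before allocation.

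**The case against.** The strongest reply is that the script is not the whole eligibility procedure. After the questions comes a separate screening for the eligibility criteria, and consent is sought only from those still eligible. Read naturally, that is a check against the criteria themselves, arrhythmia included. The script also omits the age limit and the ability to speak English, and expired CO has its own step, so eligibility already depends on more than these questions. Every participant is required to meet the criteria, and not every step has to list each of them again. K2 or K7 is a natural place for an itemised cardiac history. Finally, question 7 opens with a broad phrase about significant cardiac conditions, to which someone with a recent serious arrhythmia might well answer yes.

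Much of this stands. It rules out any claim that an arrhythmia would go undetected, and it means that nothing can be said about the attachments. Two things survive it. First, exclusion 5 uses the same broad phrase and the same list, and then adds arrhythmia as a further alternative, so the sponsor's own wording does not treat it as already covered. Second, a general requirement to meet the criteria does not say how this one is ascertained, and the only cardiac question shown leaves it out.

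A reader might infer that people with a recent serious arrhythmia have been, or will be, enrolled, and that participants already in the trial should be reviewed. The documents do not support either step. They describe other checks that may catch the condition, and they report no such enrolment.

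**Conclusion.** The mismatch is certain on the text: in both copies, question 7 asks about 4 of the 5 cardiac items in exclusion 5 and omits serious arrhythmia. In the text available, no other step names it. Whether anyone would be wrongly admitted is possible but not shown. That would require the general screening, the medical history and the unseen attachments all to miss it, and the candidate not to mention it when asked about cardiac conditions.

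The documents give no arrhythmia prevalence, so no number of affected candidates is offered. The point is a minor patient-safety consistency correction. It does not bear on sample size, power or the analysis, and it does not show that the exclusion criterion itself is wrong. The conclusion assumes that question 7 is read out roughly as written. It would shrink to a missing cross-reference if K2 or K7 already contains the item.

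**What to change.** Add serious arrhythmia to question 7 in D2, 2.c, Step 2 and in E1, Step 2, so that both ask about all five items of exclusion 5 over the same 6 months. If the Baseline Interview (K2) or the Screening Log (K7) already asks about arrhythmia, citing that item at Step 2 would do instead.

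The cost is one phrase in each of two places, or one cross-reference. The eligibility criteria, visit schedule, sample size and analysis stay as they are. No retrospective review of participants is called for on this evidence.
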